Appendix 2. Definition and Use of Visit Windows in Reporting

Visit windows defined in Table 3 will be used for longitudinal efficacy variables. For TSS, ISGA, %BSA in-person assessment, these visit windows will be used for sensitivity analysis.

Table 3. Visit windows for longitudinal efficacy variables

Visit Label	Target Day	Definition [Day window]
Screening		up to -1
Baseline	Day 1, Baseline	Day 1
Week 1	8	Days 2 to 11
Week 2	15	Days 12 to 18
Week 3	22	Days 19 to 25
Week 4	29	Days 26 to 32
Week 5	36	Days 33 to 39
Week 6	43	Days 40 - last dose + 10 days

Note: Participants will have an end-of-study (follow-up) by phone at least 28 days after the last study dose.

Below visit windows in Table 4 will be used for non-longitudinal efficacy variables.

Table 4. Visit windows for non-longitudinal efficacy variables

Visit Label	Target Day	Definition [Day window]
Screening		up to -1
Baseline	Day 1, Baseline	Day 1
Week 6/EOT	43	Day 2 - last dose + 10 days

Note: Participants will have an end-of-study (follow-up) by phone at least 28 days after the last study dose.

If two or more visits fall into the same window, keep the one closest to the Target Day. If two visits are equaled distant from the Target Day in absolute value, the later visit should be used.

Safety analysis will follow Pfizer standards.

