5.3. Methods to Manage Missing Data

5.3.1. Binary Endpoints

For non-longitudinal binary endpoints, there is no imputation for missing data, data at Week 6 or EOT will be included in the analysis.

For longitudinal binary endpoints analyzed at each scheduled visit separately, participants with missing data at a time point for any reason will be defined as MR-NR at that time point in the intervention period.

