6.1.2. Sensitivity Analyses

Two sensitivity analyses will be performed for the percent change from baseline in the TSS at Week 6 based on HVP in-person assessment.

1. Observed cases: Principal Stratum estimand will be used. The data after an intercurrent event discontinuation of study intervention, if collected, will be excluded, only no-missing observed cases in-person assessment at Week 6 (based on window definition in Table 3) will be included in the analysis. No imputation for missing data. ANOVA ([Section 5.2.1](#)) will be used. The LSM along with the corresponding SE for each treatment group, LSM difference along with the corresponding SE, 90% CI, and 1-sided p-value will be presented. The data after an intercurrent event, if collected, will be excluded, observed cases at Week 6 will be included.

2. Multiple imputations: Hypothetical estimand will be used. The data after an intercurrent event discontinuation of study intervention, if collected, will be excluded, observed cases in-person assessment at Week 6 (based on window definition in Table 3) will be included in the analysis. Missing TSS at Week 6 will be imputed using the method of MCMC multiple imputation under MAR assumption. Multiple imputation and subsequent analysis will involve the following four principal tasks:

- 1) Calculate the total number of missing values to be imputed by MCMC (nmiss) for Week 6 value.
- 2) Create a data set, one for each treatment group, of participants with observed values and those needing imputation by MCMC. The missing TSS values in each data set will be filled in using the MCMC method “ $10 \times nmiss$ ” times to generate “ $10 \times nmiss$ ” data sets. The resulting data sets for each treatment group will be combined into one complete data set by imputation. The imputed values will be rounded to the nearest integer of 0 - 12.
- 3) For each complete data set, derive % change from baseline in TSS at Week 6. The estimated treatment effect and its standard error for each complete data set will be calculated using ANOVA ([Section 5.2.1](#)).
- 4) Combine the estimated treatment effects and standard errors from the above into a single inference using Rubin’s formulae as implemented in SAS PROC MIANALYZE.

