6.2.2. ISGA Success at Week 6/EOT based on In-person Assessment

- Estimand strategy: while-on-treatment, Estimand 1 ([Section 2.1.2](#))
- Analysis set: FAS ([Section 4](#))
- Variable: ISGA success at Week 6/EOT based on in-person assessment
- Analysis method: Normal approximation to binomial
- Intercurrent event: all data after an intercurrent event of discontinuation of study intervention will be excluded, data at Week 6 or EOT will be included;
- P-value from normal approximation test, the estimate of proportion, difference in proportion and the corresponding 90% CI of participants with response at Week 6/EOT between crisaborole ointment, 2% versus vehicle will be presented. Proportions of response (\pm SE) will also be presented graphically by treatment group.

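### Does the SAP promise a Week 6-window sensitivity analysis of in-person ISGA and %BSA that it never defines?

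*SAP*

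**What the plan says.** SAP Appendix 2 sets out two schemes of visit windows. Table 3, for longitudinal variables, gives Week 6 as "Days 40 - last dose + 10 days". Table 4, for non-longitudinal variables, gives Week 6/EOT as "Day 2 - last dose + 10 days". Of the Table 3 windows the appendix adds: "For TSS, ISGA, %BSA in-person assessment, these visit windows will be used for sensitivity analysis".

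SAP Section 6.1.2 is the only place that defines such analyses: "Two sensitivity analyses will be performed for the percent change from baseline in the TSS at Week 6 based on HVP in-person assessment". Its first item is an observed-case analysis, in which "only no-missing observed cases in-person assessment at Week 6 (based on window definition in Table 3) will be included in the analysis". Its second is multiple imputation of missing Week 6 TSS.

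For in-person ISGA and %BSA, Sections 6.2.2, 6.2.4 and 6.2.6 give the main Week 6/EOT analysis and nothing more. Section 6.2.2, for example, has "Variable: ISGA success at Week 6/EOT based on in-person assessment". In Appendix 1, sensitivity rows appear only under in-person TSS.

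On missing binary data, Section 5.3.1 has two rules. The first is "For non-longitudinal binary endpoints, there is no imputation for missing data, data at Week 6 or EOT will be included in the analysis". The second, for longitudinal binary endpoints, is that "participants with missing data at a time point for any reason will be defined as MR-NR at that time point in the intervention period", where MR-NR means that a missing response counts as non-response.

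**The concern.** Appendix 2 names three endpoints and speaks of them as settled, yet only one has an analysis to go with it. Redaction is not the reason: Sections 6.2.1 to 6.2.7 and the relevant Appendix 1 rows are legible.

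The gap looks material because the two window schemes hold different people. An early-termination visit before Day 40 counts in the main analysis but falls outside the Table 3 Week 6 window. Any analysis on that window therefore needs a rule for participants who have no value in it. Leaving them out and counting them as failures can give different answers. If the rule were picked after unblinding, it could be picked for its result, and without multiplicity control (protocol Section 9.1.2) only the SAP text guards against that.

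**Working it through.** **No stated figure turns on this point.** The plan's only sample-size figure is for the primary TSS comparison (protocol Section 9.2): 35 per arm, difference 22, standard deviation 35, one-sided 5%, power at least 80%. By the normal approximation, 22 / (35 × √(2/35)) = 2.63; 2.63 − 1.645 = 0.985; power = Φ(0.985) = 83.8%. It reproduces, and nothing below touches it.

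**Who is affected.** The Table 3 Week 6 window is empty when last dose + 10 < 40, that is, when the last dose is on or before Day 29 (29 + 10 = 39). Later leavers drop out of it only if their visit comes before Day 40.

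**What the SAP provides for each in-person endpoint.**

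| Place in the SAP | TSS | ISGA | %BSA |
|---|---|---|---|
| Section 6 | two sensitivity analyses (6.1.2) | main only (6.2.2, 6.2.4) | main only (6.2.6) |
| Appendix 1 | two sensitivity rows | none | none |
| Table 1, version 4 change | sensitivity analyses added | not mentioned | not mentioned |
| Appendix 2 sentence | named | named | named |

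The three sources agree with one another. The odd one out is a windowing note.

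**Which rule would apply if the analysis were run.**

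1. Section 2.1.2 classes in-person ISGA and %BSA as non-longitudinal, under Estimand 1.
2. Section 5.3.1 gives no imputation for non-longitudinal binary endpoints. That is observed cases.
3. MR-NR is written for longitudinal binary endpoints. Section 5.2.2 ties it to Estimand 2, whose variable in Section 2.1.2 is a response read from photographs. In-person ISGA is not one.
4. Multiple imputation in Section 6.1.2 is written for TSS, with rounding to its 0 to 12 scale.
5. For %BSA, Section 5.3.2 uses observed cases for the main non-longitudinal analysis, and Section 6.1.2 item 1 supplies the template.

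**How far the choice could matter for ISGA.** All counts here are assumptions, because the current documents give no early-termination rate. Take 35 per arm, 10 responders on crisaborole and 5 on vehicle, and 7 early leavers (10% of 70), none of whom responded. With Z = (p1 − p2) / √(p1(1−p1)/n1 + p2(1−p2)/n2):

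- MR-NR, 10/35 vs 5/35: 0.1429 / 0.0966 = 1.479, one-sided p = 0.070 for every split.
- Observed cases, 10/(35−a) vs 5/(35−b), where a and b are the leavers on crisaborole and vehicle:

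| Leavers (a vs b) | Proportions | One-sided p |
|---|---|---|
| 5 vs 2 | 10/30 vs 5/33 | 0.044 |
| 4 vs 3 | 10/31 vs 5/32 | 0.058 |
| 3 vs 4 | 10/32 vs 5/31 | 0.075 |
| 2 vs 5 | 10/33 vs 5/30 | 0.097 |

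Of these four splits only 5 vs 2 crosses 5%. If one of the five crisaborole leavers had responded, it no longer does: 9/30 vs 5/33 gives 0.077, and MR-NR at 9/35 vs 5/35 gives 0.114.

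If leaving is equally likely in both arms, the chance that five or more of the seven are on crisaborole is hypergeometric: 0.161 + 0.047 + 0.006 = 0.214.

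**Null rejection averaged over all splits of seven leavers.** Exact binomial enumeration, 30% overall response in both arms, reject if Z > 1.645:

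| Assumption | Observed cases | MR-NR |
|---|---|---|
| Leavers all fail | 5.9% | 4.9% |
| Leaving unrelated to response | 5.5% | 5.5% |

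With complete data on 35 per arm the same test rejects 5.3% of the time, so the choice of rule moves the average by no more than one point.

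**The case for a change.** The strongest reply is that the no-imputation sentence in Section 5.3.1 is worded for data at Week 6 or EOT, which is the Table 4 scheme, whereas the Appendix 2 sentence puts ISGA on the longitudinal windows. Section 5.2.2 even uses ISGA success at Week 6 as its example when it describes MR-NR. An analyst could therefore argue for either rule. Under a fixed unfavourable split the difference is larger than the average suggests: with 5 vs 2 leavers who all fail, observed cases reject 8.0% of the time under the null and MR-NR 4.9%.

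Part of this stands. The Appendix 2 sentence is loose, and the SAP does not say in one line which rule a Week 6-window ISGA analysis would use. But the Section 5.2.2 example sits in a paragraph on longitudinal endpoints that closes by naming Estimand 2, so it does not carry over to the in-person score. The 8.0% is conditional on one split; the reverse split, 2 vs 5, gives 3.4% and 4.9%. Neither rule is better throughout: observed cases suits leaving that is unrelated to response, and MR-NR suits leaving that means failure. Adding MR-NR would be a trade-off, not a repair. Settling the rule after seeing results would also go against protocol Section 9.4, which requires the SAP to be final before any analysis.

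**Conclusion.** This is a clerical inconsistency, and no change to the plan follows. One sentence in a windowing appendix names two endpoints more than the analyses defined elsewhere, and the natural reading is that the sensitivity analyses concern TSS. An analyst who nevertheless ran the in-person ISGA or %BSA version would sensibly use observed cases.

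Followed as written, the plan leaves the primary TSS analysis, its two sensitivity analyses and every main secondary analysis intact. The interim decision criterion also rests on the primary endpoint (SAP Section 7). What is exposed is at most a supplementary look at secondary endpoints in a proof-of-concept trial.

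In the assumed example the choice of rule changes the 5% reading only when at least five of seven leavers are on crisaborole (21% at equal risk) and none of them responded. These sizes rest on assumed responder counts, an assumed seven leavers and equal risk of leaving. The textual conclusion rests on none of them.

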Appendix 3. Total Sign Score (TSS)

The TSS is an assessment of the severity of SD skin lesions. Each of the 4 clinical signs (erythema, papulation/elevation [excluding papulation due to lipodermatosclerosis or varicose veins], superficial erosion/denudation, and scaling) across all the treatable SD

lesions will be rated using the 4-point severity scale (ranging from 0 to 3 points). The four sub scores are summed to create the TSS, 13-point scale; ranging from 0 to 12 points, with a higher score representing a higher disease severity. TSS is considered missing if one or more item is missing.

Appendix 4. Investigator's Static Global Assessment (ISGA)

The ISGA, a five-point global assessment of AD severity, will be assessed at times specified in the Study Procedure section of study protocol to characterize subjects' overall disease severity across all treatable AD lesions (excluding the scalp).

The ISGA will be a static evaluation without regard to the score at a previous visit. It must be completed by a clinical assessor blinded for treatment arms. Every effort should be made to ensure that all ISGA assessments for a given subject are done by the same qualified individual throughout the study.

Table 5. ISGA Score

[figure not shown]
[figure not shown]
Score	Grade	Definition
0	Clear	Minor residual hypo/hyperpigmentation; no erythema or induration/papulation; no oozing/crusting
1	Almost Clear	Trace faint pink erythema, with barely perceptible induration/papulation and no oozing/crusting
2	Mild	Faint pink erythema with mild induration/papulation and no oozing/crusting
3	Moderate	Pink-red erythema with moderate induration/papulation with or without oozing/crusting
4	Severe	Deep or bright red erythema with severe induration/papulation and with oozing/crusting

* The ISGA will exclude scalp from the assessment/scoring

[figure not shown]
CCI

CCI

CCI

CCI

CC|

[figure not shown]
[figure not shown]
CCI

[figure not shown]
[REDACTED]

Detailed analysis of the DLQI

CCI

Appendix 11. List of Abbreviations

Abbreviation	Term
AE	adverse event
ANCOVA	analysis of covariance
ANOVA	analysis of variance
AR[1]	first order autoregressive
BID	twice daily
BSA	Body surface area
CI	confidence interval
CSR	clinical study report
CCI	[REDACTED]
ECG	electrocardiogram
eCRF	electronic case report form
CCI	[REDACTED]
CCI	[REDACTED]
HVP	home visit practitioner
IA	Interim analysis
ICF	informed consent form
ISGA	investigator's static global assessment
LPLV	last participant last visit
LSM	least-squares mean
MAR	missing at random
MMRM	mixed-effects model with repeated measures
MR-NR	missing response as non-response
N/A	not applicable
CCI	[REDACTED]
CCI	[REDACTED]
CCI	[REDACTED]
SAE	serious adverse event
SAP	statistical analysis plan
Std	Standard deviation
SD	stasis dermatitis
CCI	[REDACTED]
SE	standard error
TCI	Topical Calcineurin Inhibitors
TCS	Topical Corticosteroids
TEAE	treatment emergent adverse event
TSS	total sign score
ULN	upper limit of normal
